## 5.13 Safety Analyses

The safety analyses will be presented by treatment received for the Safety Analysis Set.

### 5.13.1 Adverse Events

Treatment-emergent adverse events (TEAEs) are reported according to protocol as any AE that has an onset on or after the dose of study drug or any pre-existing condition that has worsened on or after the first dose of study drug through 14 days following last dose of study drug. The following TEAE flag will be applied to distinguish AEs from TEAEs:

- Any AE that has a start date and time on or after the first dose of study drug and before last dose of study drug + 14 days

A treatment-related AE is defined as an AE as being possibly related or related to the study drug. If an AE has missing relationship it is assumed to be related to the study drug for analysis purposes.

Maximum severity will be assumed for an AE with missing severity.

The following tables will be presented for AEs incidence and/or number of events will be reported as appropriate:

- Overall summary of AEs:
  - TEAEs
  - Treatment-related TEAEs
  - Treatment-emergent serious adverse events (TESAEs)
  - Treatment-related TESAEs
  - TEAEs by severity
  - TEAEs leading to study discontinuation
  - Deaths
- TEAEs by system organ class and preferred term
- Treatment related TEAEs by system organ class and preferred term
- TESAEs by system organ class and preferred term
- TEAEs by system organ class, preferred term and maximum severity
- TEAEs by system organ class, preferred term and strongest relationship
- TEAEs leading to study discontinuation by system organ class and preferred term
- Listing of Serious AEs.
- Listing of Deaths.

Adverse event incidence is counted only once per system organ class and once per preferred term. The number and percent of patients experiencing events are reported. Outputs reported at maximum severity or strongest relationship show the highest severity/relationship reported by a patient per system organ class and preferred term.

In addition to the above summary tables, relative risks for the occurrence of any AE (i.e., at least 1 AE) during the course of the study as well as for each system organ class/preferred term will be estimated for each LB-102 dose vs placebo via a log-binomial regression model. For such analysis, the binary indicator for the presence of a given system organ class/preferred term (or any AE) will be used as response and the treatment group will be the only covariate, whose estimated regression coefficient will be exponentiated to return the associated relative risk, alongside their 95% CI and p-values. To such aim, the following sample SAS code will be used:

```
ods output estimates = rr;
proc genmod data =  descending;
  by aedecod aeterm;
  class subjid trt01an;
  model ae_binary = trt01an / dist = binomial link = log;
  estimate 'RR LB-102 50 mg vs. Placebo' trt01pn 1 0 0 -1 / exp alpha = 0.05;
  estimate 'RR LB-102 75 mg vs. Placebo' trt01pn 0 1 0 -1 / exp alpha = 0.05;
  estimate 'RR LB-102 100 mg vs. Placebo' trt01pn 0 0 1 -1 / exp alpha = 0.05;
run;
```

The above code assumes that the TRT01PN variable is ordered such that placebo is the last arm (i.e. TRT01PN = 4) and the others are sorted in ascending order, lowest to highest, and that AEDECOD and AETERM are the system organ class and preferred term variables, respectively.

All AEs will be listed.

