- Important note: Free T4 will be measured only if the result for TSH is abnormal.
- 5. Standard 12-lead ECGs (in triplicate) will be performed after the patient has been supine and at rest for ≥5 minutes. The captured ECGs must be separated by at least 1 minute. A central ECG service will be utilized to review all ECGs in order to standardize interpretations for the safety analysis. In addition, ECG results will be evaluated at the investigational site to monitor safety during the trial. Any Screening ECG with abnormal result(s) considered to be clinically significant should be repeated to confirm the finding(s) before excluding the patient from the trial. Patients will be randomized based on Screening ECG results from the central reader and Baseline ECG results from the trial site. If the Baseline ECG results from the central reader, when available, indicate a QTcF >450 msec at Baseline, the Investigator must contact the Medical Monitor to discuss the patient's continued participation in the trial. ECGs scheduled for the same visit as blood samples are to be completed before blood is drawn.
- Vital signs will include body temperature, SBP, DBP, and heart rate. Blood pressure and heart rate will be measured in the following order: supine, sitting and standing after the patient has been in each position for at least 3 minutes. Vital signs scheduled for the same visit as blood sample have to be completed before blood is drawn.

Confidential Page 56 of 102

- The recording of AEs is to start immediately after the ICF is signed and up to 14 days after the end of EoT.
- PK analyses will include the First 60 randomized patients regardless of cohort. PK blood samples will be collected on Day 1, 8, and 21 during the following timepoints after the morning dose: 15 minutes, 30 minutes, 1, 2, 3, 4, 8, and 24 hours. See protocol Section 8.3. On Day 1 only, a pre-dose PK blood sample will be collected. Samples are collected after ECGs and vital signs. The total volume of blood to be collected during the Screening, treatment, and End of Stabilization period is 161 mL. Approximately 21 mL of blood will be collected during the Screening Visit, 130 mL will be collected during the 28-day Treatment Period, and 10 mL will be collected during the End of Stabilization period.
- w. On Day 29 patients are to be started on standard antipsychotic medication as prescribed by the Investigator.

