7.2.10 Visit 6 (Study Day 28)

On Study Day 28, all assessments should be performed on the same day; the last day of study drug dosing is Day 28 and, if possible, when any patient discontinues prior to this visit, the following assessments will be performed:

• Recording of concomitant medications (e.g., prescription and nonprescription medications)

Confidential Page 62 of 102

- Full physical examination (if applicable)
- Bodyweight, BMI (derived programmatically from body weight and height measurements), and waist circumference
- Vital signs
- Resting 12-lead ECG (triplicate, further information in Section 8.2.3)
- Collection of blood and urine samples for clinical laboratory tests. Additional information is presented in the footnotes to the SoA (Table)
- Study drug administration
- Urine pregnancy test for all females of childbearing potential
- Assessment and recording of AEs
- PANSS. PCRS must be administered before PANSS
- CGI-S
- C-SSRS
- AIMS, 3 to 6 hours post-dose
- BARS, 3 to 6 hours post-dose
- SAS, 3 to 6 hours post-dose
- Cogstate test

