7.2.11 Stabilization Period (Study Days 29 Through 33)

Patients are to remain inpatient and be restabilized on standard-of-care antipsychotics, which may be started on Day 29. No other assessments are scheduled, and therefore no formal visits are shown in the SoA. However, any AEs observed or reported and concomitant medications may be recorded. If any assessments are required in order to evaluate an AE, an unscheduled visit may be conducted at the discretion of the PI.

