7.2.12 Visit 7 (Study Day 33)

On Study Day 33 (or the last day of stabilization if it occurs before Day 33) the following assessments will be conducted:

- Recording of concomitant medications (e.g., prescription and nonprescription medications)
- Urine pregnancy test for all females of childbearing potential (Table)
- Assessment and recording of AEs
- C-SSRS

Confidential Page 63 of 102

Based on known PK properties of LB-102, it is expected that within 5 days of the end of the Study Treatment Period, plasma concentration of LB-102 and its metabolites is expected to be minimal.

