10.4.5.2 Adverse Events

AEs will be characterized by type, severity, seriousness, and relationship to treatment. AEs will be coded by preferred term and system organ class (SOC) using Medical Dictionary for Regulatory Activities (MedDRA) Version 23.0.

The incidence of TEAEs (number and percent of patients reporting the AE at least once during the study), SAEs, AEs related to study treatment, SAEs related to treatment, and AEs leading to study discontinuation will be summarized by treatment.

A TEAE is defined as any AE that has an onset on or after the dose of study drug, or any pre-existing condition that has worsened on or after the first dose of study drug.

Confidential Page 84 of 102

Any AE commencing after the last dose of study drug plus 14 calendar days will not be considered treatment-emergent.

The incidence of TEAEs and treatment-related AEs will also be summarized by maximum severity and strongest relationship to study drug by MedDRA primary SOC and preferred term. The summary will include the total number and percentage of patients reporting a particular event as well as the total number of events. In counting the number of events reported, a continuous event, i.e., reported more than once and which did not cease, will be counted only once; noncontinuous AEs reported several times by the same patient will be counted as multiple events.

Relative risks for the occurrence of any AE (i.e., at least 1 AE) during the course of the study as well as for each SOC/preferred term will be calculated for each LB-102 dose vs placebo alongside 95% CI and *P* values. For such analysis, a Poisson regression model with a log-link and a robust error variance will be considered, using the binary indicator for the presence of a given SOC/preferred term (or any AE) as response and treatment as the only covariate whose betas will be exponentiated to return the associated relative risk.

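### The treatment-emergent AE window and the AE relative risks run into the post-treatment antipsychotic period, and no between-arm AE summary is limited to blinded dosing.

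*SAP*

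**What the plan says.** - **Window.** SAP 5.13.1 defines treatment-emergent AEs from first dose "through 14 days following last dose of study drug". Protocol 10.4.5.2 agrees: "Any AE commencing after the last dose of study drug plus 14 calendar days will not be considered treatment-emergent".
- **Flag.** The programmed flag in SAP 5.13.1 is worded differently. It takes onset "on or after the first dose of study drug and before last dose of study drug + 14 days".
- **Relative risks.** SAP 5.13.1 plans log-binomial "relative risks for the occurrence of any AE (i.e., at least 1 AE) during the course of the study", and for each system organ class and preferred term, for each LB-102 dose against placebo. Treatment is the only covariate. The matching output, Table 14.3.1.3, is titled as treatment-emergent events. Either reading includes the days after dosing.
- **End of dosing.** Protocol 7.2.10: "the last day of study drug dosing is Day 28".
- **What follows.** A footnote to the Schedule of Assessments (Protocol 7.1) says: "On Day 29 patients are to be started on standard antipsychotic medication as prescribed by the Investigator". Protocol 7.2.11 says patients are to "be restabilized on standard-of-care antipsychotics, which may be started on Day 29". Protocol 7.2.12 states that "within 5 days of the end of the Study Treatment Period, plasma concentration of LB-102 and its metabolites is expected to be minimal".
- **Contrast.** SAP 5.2.13 limits its C-SSRS ideation and behavior outcomes to double-blind treatment. The AE section has no such limit.

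**The concern.** Protocol 1.8.1 lists the effects of second-generation antipsychotics, among them extrapyramidal symptoms, sedation, weight gain, QTcF prolongation and prolactin elevation. These are also the effects of interest for LB-102. Once standard treatment starts, a placebo patient can have a first such event on another drug and be counted as a placebo case. An LB-102 patient who already had that event adds nothing, because SAP 5.13.1 counts each patient once per term. Protocol 6.7 also lifts the limits on lorazepam, benztropine and propranolol during stabilization, so this interval differs from the blinded one in more than the study drug.

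At stake is how clearly the AE tables describe LB-102 itself, given that safety and tolerability is a secondary objective. Listings show onset dates but compare no arms.

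**Working it through.** The documents give no AE rates and no planned relative risk, so there is no figure of the plan's own to reproduce. The timing comes from the documents. All the risks below are assumptions.

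**Timing, for a completer**
- Window: Day 1 to 28 + 14 = Day 42. Post-dose part: Days 29 to 42, which is 14 of 42 days (33%).
- Standard antipsychotic from Day 29: 14 of 14 post-dose days. From Day 33, the last stabilization day: Days 33 to 42, which is 10 of 14 (71%).
- For patients who stop early, the documents do not say when a standard antipsychotic restarts, so no share can be computed.

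**End day.** Compared by date, onset before last dose + 14 days ends at Day 41, leaving 13 post-dose days. The SAP's own definition and Protocol 10.4.5.2 both include Day 42, which is the nominal final visit. If the flag is applied to date and time, only Day 42 onsets at or after the clock time of the last dose are lost.

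**Dilution.** Let p1 and p0 be the risks during dosing on LB-102 and placebo. Let q1 and q0 be the risks of a first event in the following 14 days among patients without one so far.

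RR = [1 − (1 − p1)(1 − q1)] / [1 − (1 − p0)(1 − q0)]

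If q1 = q0 = q, the risk difference becomes (1 − q)(p1 − p0).

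Assumed uncommon term, p1 = 10%, p0 = 3% (RR 3.33, difference 7.0 points):

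| q | LB-102 | Placebo | RR | Difference (points) |
|---|---|---|---|---|
| 2% | 1 − 0.90 × 0.98 = 11.80% | 1 − 0.97 × 0.98 = 4.94% | 2.39 | 6.86 |
| 5% | 1 − 0.90 × 0.95 = 14.50% | 1 − 0.97 × 0.95 = 7.85% | 1.85 | 6.65 |
| 10% | 1 − 0.90 × 0.90 = 19.00% | 1 − 0.97 × 0.90 = 12.70% | 1.50 | 6.30 |

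Assumed any-AE risk, p1 = 60%, p0 = 50% (RR 1.20): q = 2%, 5%, 10% and 20% give 1.19, 1.18, 1.16 and 1.13.

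**Unequal post-dose risk**
- p 15% vs 5%, q 5% on LB-102 and 15% on placebo: both arms reach 1 − 0.85 × 0.95 = 19.25%, so RR goes from 3.00 to 1.00.
- p 10% vs 5%, same q: 14.50% / 19.25%, so RR goes from 2.00 to 0.75, a reversal.
- p 60% vs 50%, q 10% on LB-102 and 5% on placebo: 64.0% / 52.5%, so RR goes from 1.20 to 1.22, slightly away from 1.

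**The case against.** **The effect is confined to AE-term tables.** A reader might infer that the whole safety comparison is diluted. The Schedule of Assessments does not support that. SAS, BARS, AIMS, laboratory tests including prolactin, BMI and waist, vital signs and ECGs are last scheduled at Day 28 or early termination. New prolactin or weight AEs are also less likely to be found once nothing is scheduled to detect them. This stands.

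**The direction is conditional.** A reader might infer that the window always pulls toward no difference because another drug is given equally in all arms. The schedule footnote leaves the choice to the investigator, and Protocol 7.2.11 makes a Day 29 start permissive, so agent, dose and timing may differ by arm. That the drug is open-label is also an inference. This stands.

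**The size is hypothetical.** At q = 10%, the example gives placebo patients more than three times their assumed 28-day risk in half the time. On the difference scale, most of the excess stays visible in the planned incidence tables. This stands.

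**Attribution already filters.** Treatment-related tables are planned, and Protocol 9.1.6 allows an event to be judged unrelated when concomitant therapy explains it. This helps only in part. The same section treats temporal association as enough for a plausible link in analysis, and the SAP sets missing relationship to related.

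**A tighter main window would lose information.** Ending the main window at the antipsychotic start could cut a completer about 24 hours after the last dose. With Phase 1 mean half-lives of 11.933 to 14.146 hours (Protocol Table 14.1), 0.5^(24/11.933) = 25% to 0.5^(24/14.146) = 31% of the drug would remain. This is a good reason to add a table and keep the existing one.

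**The relative risks are descriptive, and the SAP follows the protocol's window.** Both are true, and both limit the weight of the point.

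**Conclusion.** The point holds as a gap in presentation. For a completer, up to 14 of 42 days in the TEAE window and the relative-risk period may be spent on a standard antipsychotic, and no between-arm AE summary isolates blinded dosing. If post-dose AE risk is similar across arms, relative risks for uncommon preferred terms shrink noticeably (3.33 to between 2.39 and 1.50 in the assumed example), while risk differences barely change (7.0 to between 6.9 and 6.3 points). Any-AE relative risks change little. If post-dose risks differ, the distortion can go either way, even to a reversal. The timing is documented for completers; every rate is assumed.

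The documents do not support saying that a real excess will be hidden, or that 14 days of AE collection is wrong. Separately, the one-day mismatch between the SAP flag and both stated definitions is a plain inconsistency. Overall this is a cheap improvement.

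**What to change.** 1. Keep the 14-day window and all planned TEAE tables.
2. Add a period flag. Show TEAE incidence by system organ class and preferred term, and the log-binomial relative risks, also for onset from first dose up to the recorded start of standard antipsychotic after the last dose. Show later onsets separately as post-treatment.
3. State what ends the first period when no restart is recorded; the end of the TEAE window is a natural choice. Exempt this start date from SAP 5.2.6, which would set a missing start date for an ongoing medication to the first dose and empty the period.
4. Change the flag to onset on or before last dose + 14 days, compared by calendar date, so that Day 42 onsets count as in Protocol 10.4.5.2.
5. Reconcile the schedule footnote with Protocol 7.2.11 on whether the Day 29 start is required or permitted.

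Cost: one derived flag and a few extra tables, from data already collected. No event is dropped. The log-binomial models will have fewer events in the on-treatment version, so more terms may fail to converge.

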6.7 Prior and Concomitant Medications

All prescription, nonprescription medications (e.g., over-the-counter [OTC]) drugs and herbal supplements) and non-medical treatments starting from 30 calendar days before Screening until end of the study must be recorded in source documents and the eCRF. For each medication, documentation should list the trade or generic name, the total daily dose including units (or the dose, units, and scheduled and actual frequency of administration if the medication is not taken daily), the route of administration, and the reason for use.

Changes, additions, or discontinuations to medications will be assessed and recorded in the eCRF during each study visit. All as-needed prescriptions should be converted to reflect actual dose taken per day.

Starting on the first day of the screening phase, after written informed consent for the study has been provided, all antipsychotic or other psychotropic medications will be stopped with clinically appropriate titration down as per the Investigator's clinical judgment. Patients will be

Confidential Page 49 of 102

instructed not to take any medication(s) during the conduct of the study unless approved by the Investigator. Any patient unable to be safely discontinued from current antipsychotic therapy or other psychotropic medications will not be eligible for the study. Any treatment other than the study treatment given will be considered a concomitant medication and will be documented in the eCRF. Any patient requiring emergency treatment with prescription or nonprescription medication during the screening phase through the EoS Visit will be approved by the Investigator. If the Investigator determines that the patient requires medication during the study, the Medical Monitor must be contacted within 24 hours.

Psychotropic medications are prohibited except for lorazepam as needed for agitation, restlessness, irritability, or hostility; zolpidem, zaleplon, or eszopiclone for insomnia; diphenhydramine or benztropine for EPS; and propranolol for akathisia.

Within the daily limits shown in 2, lorazepam, benztropine, and propranolol are not allowed on as needed basis; every administration must be considered and approved by the Investigator prior to administration.

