9.1.5 Assessment of Severity

Each AE will be classified according to the following criteria:

Mild: The AE does not interfere in a significant manner with the patient's

normal level of functioning.

Moderate: The AE produces some impairment of functioning, but is not

hazardous to the patient's health.

Severe: The AE produces significant impairment of functioning or

incapacitation and is a definite hazard to the patient's health.

Severity versus Seriousness: Severity is used to describe the intensity of a specific event while the event itself may be of relatively minor medical significance (such as severe headache). Severity is not the same as "seriousness," which is based on patient/event outcome at the time of the event.

When changes in the severity of an AE occur more frequently than once a day, the maximum severity for the experience should be noted. If the severity category changes over several days, those changes should be recorded as separate AEs (with distinct onset dates).

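### The TEAE flag reads the start date and time alone, so a screening AE that eases after first dose counts as treatment-emergent; its end point also conflicts with the plan's own 14-day window

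*SAP*

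**What the plan says.** **Definition and flag.** SAP 5.13.1 defines a TEAE as an AE that starts once dosing has begun, or "any pre-existing condition that has worsened on or after the first dose of study drug through 14 days following last dose of study drug". It then states the flag to be applied, which selects any AE with a "start date and time on or after the first dose of study drug and before last dose of study drug + 14 days". Protocol 10.4.5.2 has the same two limbs, joined as alternatives, and closes the window by exclusion: "Any AE commencing after the last dose of study drug plus 14 calendar days will not be considered treatment-emergent".

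**How AE records arise.** Protocol 9.1.5 says: "If the severity category changes over several days, those changes should be recorded as separate AEs (with distinct onset dates". It makes no distinction between worsening and improvement. There is one exception: "When changes in the severity of an AE occur more frequently than once a day, the maximum severity for the experience should be noted".

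**Why pre-dose AE records exist.** AEs are recorded from consent (Protocol 8.2.5 and 9.2.1). From the first day of screening, "all antipsychotic or other psychotropic medications will be stopped with clinically appropriate titration down" (Protocol 6.7). Screening lasts up to 7 days and can be extended by 7. Lorazepam, benztropine and propranolol are permitted from screening on, and the AE behind their use is to be recorded (Protocol 6.7). Illnesses present at consent go to medical history, but their worsening during the study is an AE (Protocol 9.2.1).

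**Counting.** SAP 5.13.1 counts a patient once per system organ class and once per preferred term. Protocol 10.4.5.2 counts an unbroken event once when events are totalled; SAP 5.13.1 does not repeat this. SAP section 8 lists a change of AE model but no change to the TEAE rule or its window.

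**The concern.** The flag looks at each record in isolation. The protocol splits one continuing condition into several records, each with its own onset date, whenever the severity category changes over several days. A condition that began before first dose and then improves can therefore enter the TEAE tables as though treatment had brought it on.

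The terms most exposed are those that washout may produce or that the permitted medications treat: insomnia, agitation, extrapyramidal symptoms and akathisia. For a dopamine antagonist compared with placebo these matter. The flag feeds the TEAE tables, including those for treatment-related events, maximum severity and strongest relationship. It also feeds the relative risks with confidence intervals and p-values for each dose against placebo, which the SAP's output list titles as a TEAE table.

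**Working it through.** The plan gives no figure on this point, so there is none to reproduce. The check has three parts.

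**1. Trace one case.** Moderate insomnia starts on Day −3, is ongoing at first dose on Day 1, and becomes mild on Day 3 without resolving.

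- Protocol 9.1.5 produces two records: moderate with onset Day −3, and mild with onset Day 3.
- The SAP flag selects the Day 3 record, because its start lies after first dose and inside the window.
- Under the written definition the worsening limb is not met, but the onset limb is, because the Day 3 record has a post-dose onset.
- The once-per-term rule does not remove the patient: this is the only flagged record, so the patient counts as one insomnia TEAE.

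Adding the worsening limb to the flag would change nothing here. What is missing is a link from the Day 3 record to the Day −3 record and its severity.

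**2. End of the window.** With a last dose on Day 28, 28 + 14 = Day 42, the nominal End of Study visit (Protocol 7.1).

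| Rule | AE starting on Day 42 |
|---|---|
| SAP definition | included |
| Protocol 10.4.5.2 | included |
| SAP flag, read as dates | excluded |
| SAP flag, read as dates and times | included only if earlier in the day than the last dose was taken |

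SAP 5.2.6 imputes missing dates but has no rule for missing times.

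**3. Effect on a relative risk (illustration).** The documents give no AE rates for this population, so every input is assumed. Let p be the true TEAE incidence and b the share of the remaining patients whose only flagged record is a step-down. Subscript 0 is placebo and 1 is LB-102.

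Observed rate = p + b(1 − p)

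Observed RR = [p₁ + b₁(1 − p₁)] / [p₀ + b₀(1 − p₀)]

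Example at p₀ = 5%, p₁ = 10%, b = 5% in both arms: (0.10 + 0.05 × 0.90) / (0.05 + 0.05 × 0.95) = 0.145 / 0.0975 = 1.49.

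| Assumed true rates, placebo vs LB-102 | True RR | b = 2% | b = 5% | b = 10% |
|---|---|---|---|---|
| One term, 5% vs 10% | 2.00 | 1.71 | 1.49 | 1.31 |
| One term, 5% vs 15% | 3.00 | 2.42 | 1.97 | 1.62 |
| One term, 10% vs 10% | 1.00 | 1.00 | 1.00 | 1.00 |
| Any TEAE, 50% vs 60% | 1.20 | 1.19 | 1.18 | 1.16 |

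With unequal step-down rates:

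- 5% vs 10% true, b₀ = 5%, b₁ = 12%: 0.208 / 0.0975 = 2.13 (true 2.00).
- 5% vs 10% true, b₀ = 10%, b₁ = 2%: 0.118 / 0.145 = 0.81 (true 2.00).
- 10% vs 10% true, b₀ = 5%, b₁ = 10%: 0.190 / 0.145 = 1.31 (true 1.00).
- 10% vs 10% true, b₀ = 5%, b₁ = 2%: 0.118 / 0.145 = 0.81 (true 1.00).
- Any TEAE, 50% vs 60% true, b₀ = 5%, b₁ = 10%: 0.640 / 0.525 = 1.22 (true 1.20).

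With b₀ = 5%, the observed RR equals the true one at b₁ = 10.6% for 5% vs 10%, since (2 × 0.0975 − 0.10) / 0.90 = 0.106. For 50% vs 60% it does so at b₁ = 7.5%, since (1.2 × 0.525 − 0.60) / 0.40 = 0.075. Below these values the RR is understated; above them it is inflated.

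**The case against.** The best defence is that the flag works as intended given how the data are logged. A worsening also becomes a new record with its own onset date, so a start-date test does capture it, and no genuine post-dose onset inside the window is discarded, the last day apart. The flaw also needs a chain of events in one patient: an AE that arises or worsens after consent within a short screening phase, is still present at first dose, eases by a category without resolving (resolution creates no new AE), and is not accompanied by a genuine TEAE of the same term. The maximum-severity table would show the step-down record at its lower grade. All of this is correct and limits the likely size. None of it removes the misclassification when the chain does occur.

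The documents do not support several stronger readings that a reader might infer:

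- **That omitting the worsening limb from the flag is the cause.** The limbs are alternatives, and the step-down record already meets the onset limb.
- **That every change of severity makes a new AE.** Changes more frequent than once a day are recorded at maximum severity.
- **That relative risks are always pulled toward 1.** This requires similar step-down rates across arms, which no document states. If LB-102 relieves washout symptoms, step-downs may be more frequent on active treatment.
- **That event totals are inflated.** The protocol's rule on continuous events arguably still governs, since SAP 5.13.1 says that TEAEs are reported according to the protocol and section 8 declares no departure. The gap is only that the SAP does not restate it.

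The 14-day mismatch affects at most one day of onsets, and all AEs are listed, so no event disappears from the report.

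**Conclusion.** The point holds on two counts. First, a start-date flag combined with direction-neutral splitting of AE records classifies improving pre-dose conditions as treatment-emergent. Second, the flag's end point contradicts both the SAP's own definition and the protocol, with no change declared.

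The direction of the first error is not fixed. Per-term relative risks move toward 1 if step-downs are about equally common in all arms, and can be inflated or reversed if they are not. The any-TEAE relative risk moves little in every case computed (1.16 to 1.22 against a true 1.20). These figures rest wholly on assumed rates, and the actual size cannot be determined from the documents. The second error is confined to onsets on the last day of the window, but that day is the nominal End of Study visit, at which AEs are assessed. The change is worth making because the comparison by term is where the safety profile will be read and the repair uses data already collected.

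**What to change.** Replace the flag in SAP 5.13.1 with a rule in three parts:

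1. An AE is treatment-emergent if its onset is on or after first dose and on or before the calendar date of last dose + 14 days.
2. Where the record continues, without a gap, an event of the same preferred term that was present before first dose, flag it only if its severity exceeds the worst pre-dose severity.
3. In event totals, count linked records of one continuous event once, as Protocol 10.4.5.2 provides.

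Keep every record in the AE listing, so that the linking can be inspected.

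The cost is a SAP wording change and a short derivation from onset date, end date, severity and preferred term. The downside is that a same-term, no-gap linking rule has to be written and programmed. Comparing with the worst pre-dose severity is also a convention: a continuous event that had eased before first dose and later rises again, but not above its earlier worst, would not be flagged. The SAP should say so. SAP section 5 requires amendments before database lock; after that, the change belongs in the addendum for which the section provides.
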